**Figure 1. The Tack Endovascular System**

 ≥50%

 For the one PTA that reported restenosis at 6 months, all patients were Rutherford Class 4-6 which would likely correlate with a higher restenosis rate

- |                                         |                                 |
|-----------------------------------------|---------------------------------|
| 1. Guidewire Lumen                      | 10. Side port                   |
| 2. Distal Tip                           | 11. Hemostatic Valve            |
| 3. Inner Core Shaft                     | 12. Inner Core Shaft            |
| 4. Distal Inner Core Marker             | 13. Proximal Inner Core Markers |
| 5. Crimped Tack                         | 14. Guidewire Port              |
| 6. Target Band (Outer Sheath RO Marker) | 15. Unconstrained Tack          |
| 7. Outer Braided Sheath                 | 16. Middle RO Marker            |
| 8. Strain Relief                        | 17. Anchor                      |
| 9. Bifurcation Luer                     |                                 |

The Tacks are approximately 6mm in length and expand to an unconstrained diameter of 7.3 mm (See **Table 4** below). The Tack implants are designed with a relatively flat chronic outward force curve and may be used across all reference vessel diameters (RVDs) ranging from 2.5 to 6.0mm. Six Radiopaque (RO) Markers (16) as well as six pairs of Anchors (17) are located around the centerline of each Tack implant. The anchors assist in maintaining proper Tack implant position.

**Table 4. Tack Length at Various Diameters**

Diameter	Length
1.8 mm (Constrained Tack)	6.5 mm
2.5 mm RVD (Deployed Tack)	6.4 mm
6.0 mm RVD (Deployed Tack)	6.2 mm
7.3 mm (Unconstrained Tack)	6.1 mm

The delivery catheter has an effective length of 120cm. The 6F Outer Braided Sheath (7), which constrains the Tack implants, is bonded proximally to the Bifurcation Luer (9) within the Strain Relief (8). The Hemostatic Valve (11) is integrated proximally to the Bifurcation Luer. The Inner Core Shaft (3) slides within the Hemostatic Valve and has seven Proximal Inner Core Markers (13). The number of visible reference marks corresponds to the number of undeployed Tack implants remaining in the distal end of the delivery system. A soft, tapered Distal Tip (2) is bonded to the distal end of the Inner Core Shaft for ease of advancement in the blood vessel. Constrained within the Outer Braided Sheath, each self-expanding Tack implant is positioned on the Inner Core Shaft (3) between two radiopaque Distal Inner Core Markers (4) spaced approximately 7mm apart. A 1mm radiopaque Target Band (6) is located on the distal end of the Outer Braided Sheath.

The catheter is flushed prior to the procedure through the side port of the Bifurcation Luer and the Guidewire Port. Tack implant positioning is achieved prior to deployment by using as reference the Middle RO Markers on the Tack implant and the Target Band on the outer sheath. During Tack implant deployment; the Hemostatic Valve is unlocked by rotating the valve counter-clockwise. The Tack implants are individually unsheathed by pinning the Proximal Inner Core Shaft and pulling back on the outer sheath the distance between proximal inner core markers. After each deployment, the Hemostatic Valve is locked by rotating the valve clockwise, ensuring that the proximal edge of the Target Band is secured directly over a Distal Inner Core Marker. Between deployments, both the proximal inner core markers and the distal inner core markers serve to visually represent the number of remaining Tack implants in the delivery catheter.

## 5.2. PRINCIPLES OF OPERATION

A peripheral intervention of the lower extremity arteries, such as balloon angioplasty to treat stenotic or occluded arteries is performed, which would include dilatation of the artery at the target site to its full intended arterial diameter. A post-PTA angiogram is done to assess the results of the angioplasty. If optimal angioplasty results are not achieved due to one or more dissections in a lesion with less than 30% residual diameter stenosis (DS), the patient may be a candidate for treatment with the Tack Endovascular System.

Once a treatment area has been identified for the Tack Endovascular System, a 0.035" guidewire is inserted into the 6F percutaneous angiographic sheath and advanced to the targeted treatment site. The delivery catheter is then advanced to the treatment site using fluoroscopic guidance. Each Tack is deployed independently at the desired location by retracting the distal sheath which contains the constrained Tacks.

Note: For a full device and procedural description, please refer to the Instructions for Use (IFU).

### 5.3. INTENDED USE

The Tack Endovascular System is intended for use in the superficial femoral and proximal popliteal arteries ranging in diameter from 2.5mm to 6.0mm for the repair of post percutaneous transluminal balloon angioplasty dissection(s) type(s) A through F.

## 6. CLINICAL STUDY OBJECTIVES

### 6.1. PRIMARY ENDPOINTS

Safety: Freedom from the occurrence of any new-onset major adverse event(s) (MAEs) defined as index limb amputation (above the ankle), CEC adjudicated clinically-driven target lesion revascularization (CD-TLR), or all-cause death at 30 days.

Efficacy: Primary patency defined as freedom from CEC adjudicated clinically-driven target lesion revascularization (CD-TLR) and freedom from core lab adjudicated duplex ultrasound derived binary restenosis at 12 months (defined as PSVR  $\geq$ 2.5).

### 6.2. OBSERVATIONAL ENDPOINTS

Device Success: Successful deployment of the Tack(s) at the intended target site(s) and successful withdrawal of the delivery catheter. If the study device is introduced but the subject does not receive a Tack due to user error and not a device malfunction, this device will not be included in the device success assessment.

Procedural Success: Demonstrated vessel patency (<30% residual DS, by visual estimate) without the use of a bailout stent or the occurrence of MAE upon completion of the index procedure.

The following will be assessed through 36 months:

- All-cause death
- Amputation of the target limb (above the ankle)
- Clinically-driven target vessel revascularization (CD-TVR)
- Clinically-driven target lesion revascularization (CD-TLR)
- Target vessel revascularization (TVR)
- Target lesion revascularization (TLR)
- Changes from Baseline in Rutherford Classification
- Changes from Baseline in Ankle Brachial Index (ABI) measurement
- Changes from Baseline in the Peripheral Artery Questionnaire (PAQ)
- Changes from Baseline in the EQ-5D-3L quality of life questionnaire
- Changes from Baseline in the Walking Impairment Questionnaire (WIQ)
- Tack Integrity via X-ray (only performed at 12 month visit)
- Duplex Ultrasound (DUS) derived lesion and vessel patency (performed at each visit through 12 months)

## 7. CLINICAL STUDY DESIGN

This is a prospective, multi-center, single-arm, non-blinded study designed to investigate the safety and efficacy of the Tack Endovascular System in subjects with post-balloon angioplasty (post-PTA) dissection(s) type(s) A through F in the superficial femoral and proximal popliteal arteries ranging in diameter from 2.5mm to 6.0mm.

### 7.1. INVESTIGATIONAL SITES

Subjects will be enrolled at up to 40 clinical sites throughout the United States and Europe (up to 5 European sites will participate).

### 7.2. SUBJECT POPULATION

Subjects with PAD who receive PTA (with a standard or FDA-approved Lutonix drug-coated balloon) in the SFA and proximal popliteal (P1) arteries and have a resulting dissection(s) type(s) A through F are eligible for enrollment. To be enrolled, subjects must meet all inclusion criteria and not meet any of the exclusion criteria.

### 7.3. ANTICIPATED NUMBER OF SUBJECTS

It is anticipated that up to 210 subjects will be enrolled. Each clinical site can enroll a maximum of 53 patients, establishing an enrollment cap at 25% of the subject sample size.

Intact Vascular will continuously monitor each enrolled subject receiving study device treatment following PTA with a standard balloon or the FDA-approved Lutonix drug-coated balloon (DCB). Treatment with a Tack following PTA with a DCB shall not exceed 60% of subjects enrolled.

### 7.4. CLINICAL STUDY DURATION & FOLLOW-UP

The follow-up duration for each enrolled subject is 36 months. Any subject who is enrolled but does not receive at least one Tack implant will be followed for 12 months and then exited from the study (see **Section 10.3.1**).

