#### 10.3.1. ENROLLMENT (INTENT-TO-TREAT)

A subject is defined as an intent-to-treat (ITT) patient and officially enrolled in the study once the Tack Endovascular System is advanced through the introducer sheath. Subjects in whom at least one Tack is not placed, will be exited after 12 months. Subjects in whom at least one Tack is placed will be followed for 36 months.

In addition, the per-protocol (PP) population will be defined as ITT subjects with evaluable data that have met the definition for device success, excluding subjects with major deviations such as:

- A major inclusion/exclusion criterion deviation; or
- A major procedural deviation

The criteria for deviations meeting the classification of “major” will be defined before study endpoint data is available for statistical analysis. All major deviations will be adjudicated by an independent designee without visibility to study results.

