#### 10.5. BAILOUT STENTING OF TARGET LESION (POST-STUDY DEVICE)

The use of a bailout stent may occur in the event of persistent flow-limiting dissection not able to be treated with the Tack (or as otherwise required for safety of the subject). All enrolled subjects in whom at least one Tack is placed and receive a bailout stent will be followed for the duration of the study.

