#### 16.11. OBSERVATIONAL ENDPOINTS

The observational endpoints are listed in **Section 6.2** and are supportive in nature. Descriptive statistics will be calculated and may be provided in labeling if deemed informative for the user. Descriptive statistics for the purposes of labeling are defined as N, mean, standard deviation, median, interquartile range, minimum and maximum for continuous variables and number and percent of observations for categorical variables.

Standard statistical methods will be used and include the Kaplan-Meier product limit method for time to event endpoints and the Wilcoxon signed rank test for changes from baseline for endpoints compared to baseline. Statistical significance will be defined as two-sided  $\square < 0.05$ . Two sided 95% confidence intervals may be calculated for estimates. P-values and 95% confidence intervals are not intended for the labeling.

Safety endpoints will be evaluated in the sample of subjects meeting the ITT definition only. Efficacy endpoints will be evaluated in both the ITT and PP subjects.

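### ITT subjects who receive no Tack are exited at 12 months by rule, so the 24- and 36-month ITT safety results lose their later experience

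*Combined protocol and SAP*

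**What the plan says.** - **Who is ITT.** Under 10.3.1 a subject is "officially enrolled in the study once the Tack Endovascular System is advanced through the introducer sheath". Section 16.2 also requires the eligibility criteria to be met. Neither section requires a deployed Tack.
- **How long subjects are followed.** Section 7.4 opens with the general rule: "The follow-up duration for each enrolled subject is 36 months". It then makes an exception: a patient who was "enrolled but does not receive at least one Tack implant will be followed for 12 months and then exited from the study". Section 10.3.1 agrees: "Subjects in whom at least one Tack is not placed, will be exited after 12 months".
- **Tack plus bailout stent.** Section 10.5: "All enrolled subjects in whom at least one Tack is placed and receive a bailout stent will be followed for the duration of the study".
- **Horizon of the observational endpoints.** Section 6.2: "The following will be assessed through 36 months". The list includes all-cause death, amputation, TLR, TVR and their clinically driven forms, Rutherford class, ABI and the questionnaires.
- **Analysis set and method.** Section 16.11: "Safety endpoints will be evaluated in the sample of subjects meeting the ITT definition only". Efficacy endpoints are evaluated in both ITT and PP. The same section names the "Kaplan-Meier product limit method for time to event endpoints" and allows descriptive statistics to appear in labelling.
- **Early exits.** Section 12.10 keeps and evaluates data up to withdrawal. Section 16.7 summarises early exits with their reasons.

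**The concern.** After month 12 the ITT sample can contribute new data only from subjects with at least one Tack. A protocol rule does this, not chance loss, and the rule depends on what happened in the index procedure. Two subjects who both end with a bailout stent are treated differently: with one Tack placed, follow-up runs to 36 months; with none, it stops at 12.

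Kaplan-Meier assumes that censored subjects have the same later risk as those who remain. A subject in whom no Tack could be placed may not, and the plan as written gives no way to find out. No section defines a set of implanted subjects for the late results or says how this exit is to be handled. The missing-data sensitivity analyses of 16.6 are called on only for the two primary endpoints (16.8, 16.9). PP does not recover these subjects either, because it requires device success.

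At stake is how the 24- and 36-month figures are read. They would be described as ITT, and they may reach the label.

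**Working it through.** **1. The plan's own figures, to see what is touched.** One-sample exact binomial tests:
- Efficacy (goal 53%, assumed 65%, one-sided 0.025): at N = 178 the rule is at least 108 patent, with exact alpha 0.0237 and power 90.04%. The smallest N reaching 90% is 178, as stated.
- Attrition: 178 / 0.85 = 209.4, so 210, as stated.
- Safety (goal 88%, assumed 95%, one-sided 0.05): at N = 138 the rule is at least 128 event-free, with exact alpha 0.0494 and power 91.4%. The smallest N reaching 90% is 138, as stated.

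The primary endpoints fall at 30 days and 12 months, and no-Tack subjects are followed to 12 months. None of these numbers changes.

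**2. Inputs for the late results.** From the documents: N = 210, exit at 12 months, Kaplan-Meier. Assumed, because the documents do not give them:
- k = 2 to 8 subjects without a Tack, so w = k/210 = 1.0% to 3.8%;
- event-free with a Tack: 90% at 12 months and 80% at 36 months;
- event-free without a Tack: 75% and 50%;
- no other loss to follow-up.

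**3. Formulas.**
- Full ITT at 36 months, if everyone were followed: (1 − w) × 0.80 + w × 0.50.
- Kaplan-Meier as planned: [(1 − w) × 0.90 + w × 0.75] × (0.80/0.90). The first factor includes the no-Tack subjects through month 12. The second comes only from implanted subjects.
- Difference: w × (0.75 × 0.80/0.90 − 0.50) = w × 0.1667.

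**4. Results.**

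| k | w | Full ITT | Kaplan-Meier | Difference (points) |
|---|---|---|---|---|
| 2 | 1.0% | 79.71% | 79.87% | 0.2 |
| 4 | 1.9% | 79.43% | 79.75% | 0.3 |
| 6 | 2.9% | 79.14% | 79.62% | 0.5 |
| 8 | 3.8% | 78.86% | 79.49% | 0.6 |

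**5. Range.**
- If no-Tack subjects fare like the others (90% and 80%), the difference is 0 for every k.
- With 21 of 210 (10%) without a Tack and the same rates, full ITT is 77.0% and Kaplan-Meier 78.67%, a difference of 1.7 points.
- With 21 of 210 and worse no-Tack rates (60% and 30%), they are 75.0% and 77.33%, a difference of 2.3 points.

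**6. Summaries that do not use Kaplan-Meier.** Rutherford class, ABI and questionnaire changes at 24 and 36 months need a visit at that time. No-Tack subjects have none, so those tables describe implanted subjects only. The effect on those scales cannot be sized from the documents.

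**The case against.** The strongest case against is that the exit is disclosed in advance and touches little.

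- **A reader might infer that the late ITT results leave these subjects out altogether, or are simply as-treated.** The documents do not support that for time-to-event endpoints. Kaplan-Meier (16.11), with data kept up to exit (12.10), counts their events and time at risk through month 12. This objection stands: only their later experience is lost.
- **A reader might infer that exit means device failure.** It does not. The rule covers only subjects with no Tack at all, and 6.2 foresees cases due to user error. Partial failures with at least one Tack, including those given a bailout stent, are followed to 36 months. This also stands.
- **Section 7.4 might look self-contradictory.** It reads as a general rule followed by an exception.
- **Which endpoints are safety endpoints is partly inferred.** Death, amputation and clinically driven TLR are the components of the MAE definition (14.4). Section 16.11 does not assign TLR, TVR or clinically driven TVR to safety or efficacy. Rutherford class, ABI and the questionnaires are not clearly safety endpoints, so the ITT-only sentence may not reach them, although the missing late visits do.
- **Sections 12.10 and 16.7 already tabulate exits and reasons.** That makes the count recoverable. It neither supplies the missing outcomes nor tells the reader of a late estimate that the censoring is by rule.

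What remains is censoring that depends on the procedural result, in results described as ITT, with nothing in the plan to correct or disclose it beside the estimate.

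**Conclusion.** The point holds as a minor one. The 12-month exit of no-Tack subjects removes their events after month 12 from the late ITT safety results, for a reason that may be related to prognosis. Under the assumptions shown (2 to 8 of 210 without a Tack, and worse outcomes in them), the 36-month Kaplan-Meier estimate is about 0.2 to 0.6 points too favourable. The direction and size rest wholly on those assumed rates and counts.

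It would be wrong to infer that the trial's main conclusions are at risk. The 30-day and 12-month primary analyses, their sample sizes and their power are untouched. The affected endpoints are supportive. They enter labelling only if judged informative, and without p-values or confidence intervals.

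**What to change.** **Preferred.** In 7.4 and 10.3.1, keep consenting ITT subjects without a Tack in remote follow-up, by telephone or records, at 24 and 36 months. Collect vital status, index-limb amputation and revascularisation. No added visit, duplex or X-ray is needed; Table 5 schedules no imaging at those times for anyone. Decide this before the first such subject reaches month 12, because data not collected by then may be hard to recover.

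**If the exit is kept.** State in 16.11 that ITT estimates beyond 12 months censor no-Tack subjects by rule, and show their number beside each estimate. Label visit-based 24- and 36-month summaries as Tack-implanted subjects.

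**Cost.** The first option means two extra contacts for what is probably a handful of subjects, their agreement to stay in the study longer, and a possibly slightly less favourable late figure. The second is a change of text only, at the price of a narrower description of the late visit-based results.

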### 7.5. SUBJECT SELECTION

#### 7.5.1. INCLUSION CRITERIA

Subjects must meet all the following Inclusion Criteria. The response for each criterion below must be “Yes”:

1. Male or non-pregnant Female  $\geq$  18 years of age at the time of consent
2. Female subjects of childbearing potential must have a negative pregnancy test prior to treatment and must use some form of contraception (abstinence is acceptable) through the duration of the study
3. Target limb requires no additional treatment aside from the target lesion and the iliac artery(ies) during the index procedure
4. Subject has been informed of and understands the nature of the study and provides signed informed consent to participate in the study. If the subject possesses the ability to understand and provide informed consent but due to physical inability, the subject cannot sign the ICF, an impartial witness may sign on behalf of the subject

5. Willing to comply with all required follow-up visits
6. Rutherford Classification 2, 3 or 4
7. Estimated life expectancy >1 year
8. Eligible for standard surgical repair, if necessary
9. Subject is ambulatory (assistive devices such as a cane or walker is acceptable).

#### 7.5.2. ANGIOGRAPHIC INCLUSION CRITERIA

Subjects must meet all the following Angiographic Inclusion Criteria. The response for each criterion below must be “Yes”:

1. Reference vessel diameter is between 2.5 mm and 6.0 mm, inclusive (by visual estimate), and able to be treated with the Study Device implant
2. Ability to cross a guidewire (antegrade) through target lesion
3. Has a de novo or non-stented restenotic target lesion indicated for PTA treatment with a standard or FDA-approved Lutonix drug-coated balloon catheter that meets the following criteria below:

- a. 70% to 99% stenosis with a total lesion length of  $\geq 20$ mm and  $\leq 150$ mm in length (by visual estimate) or;
- b. 100% occluded with a total lesion length  $\leq 100$ mm (by visual estimate)

Notes:

A tandem lesion, defined as a lesion comprised of diseased and healthy segments, is eligible if the healthy segments are each not more than 30mm in length and all other criteria, including 3a and 3b above, are met

A combination lesion, defined as a continuous lesion with both non-occluded and 100% occluded segments, is eligible if the lesion can be treated as a single lesion and all other criteria, including 3a and 3b above, are met

- c. A non-stented restenotic lesion must meet the following criteria:
  - i. Meets criteria 3a and 3b
  - ii. No part of the target lesion has been previously treated with a drug-coated balloon
  - iii. No part of the target lesion has had more than 2 previous PTA failures
  - iv. >90 days from most recent angioplasty treatment
4. Target lesion is in the superficial femoral artery (SFA) and/or proximal popliteal artery (above the knee), located  $\geq 1$  cm below the common femoral artery (CFA) bifurcation to the distal segment of the proximal popliteal (P1) artery at the superior end of the patella
5. Presence of at least one patent (<50% DS) infrapopliteal vessel that has not been revascularized prior to index procedure
6. After PTA treatment, the target lesion has <30% residual DS *and* presence of at least one post-PTA dissection (Type A-F) (by visual estimate)
7. No evidence of aneurysm or acute thrombus in target vessel

### 7.5.3. EXCLUSION CRITERIA

Subjects must not meet any of the following Exclusion Criteria. The response for each criterion below must be “No”:

1. Rutherford Classification 0, 1, 5 or 6
2. Is pregnant or refuses to use contraception through the duration of the study
3. Previous infrainguinal bypass graft in the target limb
4. Planned amputation on the target limb
5. Systemic infection or Infection within the target limb and/or immunocompromised
6. Endovascular or surgical procedure (not including diagnostic procedures) on the target limb within 30 days prior to or within 30 days after the index procedure
7. Endovascular or surgical procedure (not including diagnostic procedures) on the non-target limb within 14 days prior to the index procedure or planned procedure within 30 days after the index procedure
8. Prior coronary artery bypass graft (CABG) or percutaneous coronary intervention (PCI) procedure within 30 days prior to the index procedure or planned CABG/PCI within 30 days after the index procedure
9. Any other previous or planned surgical or endovascular procedure (not including diagnostic procedures) within 14 days prior to or 30 days post index procedure
10. Planned atherectomy, cryoplasty, stenting or any other treatment (with the exception of a crossing device) of the target lesion other than PTA during the index procedure
11. Known coagulopathy, hypercoagulable state, bleeding diathesis, other blood disorder, or a platelet count less than 80,000/microliter or greater than 500,000/microliter.
12. Known hypersensitivity or allergy to antiplatelet or anticoagulant therapy
13. Myocardial infarction within 30 days prior to enrollment
14. History of stroke within 90 days prior to enrollment
15. Serum creatinine of >2.5 mg/dL
16. Requires treatment of tibial or outflow vessels at the index procedure, which include the P2 and P3 segments of the popliteal artery and the tibioperoneal vessels.
17. Known hypersensitivity or contraindication to nickel-titanium alloy (Nitinol)
18. Participating in another ongoing investigational clinical trial that has not completed its primary endpoint
19. Has other comorbidities that, in the opinion of the investigator, would preclude them from receiving this treatment and/or participating in study-required follow-up assessments
20. Known hypersensitivity or allergy to contrast agents that cannot be medically managed
21. Thrombolysis of the target vessel within 72 hours prior to the index procedure, where complete resolution of the thrombus was not achieved

